8.6.3 Other covariates, including confounders, effect modifiers and other variables

The following covariates will be reported as part of patient and treatment characterisation for each specific individual JAKi ingredient.

- Age at index date will be calculated. Age will be presented as a mean/median age as well as proportion of patient stratified within age groups (0-3, 4-12, 13-18, 19-40, 41-60, >60).
- Sex (male/female)
- Pre-specified indicated condition for JAKi, defined by condition recorded before index date (yes/no for each indication). Indications of JAKi will be defined by any records of the above-mentioned prespecified conditions before the first exposure of specific individual JAKi ingredient. Multiple indications are allowed. Preliminary code lists for the pre-defined indications are provided in Appendix I.
 - Atopic dermatitis
 - Juvenile idiopathic arthritis
 - o Inflammatory bowel disease
 - o Alopecia areata
 - Axial spondyloarthritis
 - Psoriatic arthritis
 - Rheumatoid arthritis
 - Unknown indication (defined as none of the predefined indications were found)
- Time from first indication to first JAKi initiation, estimated separately for each pre-specified indication (more than one per patient is possible) and presented in months
- Duration of index JAKi treatment era (months)
- Prior use of other JAKi (yes/no)

In addition, a large-scale characterisation for identifying potentially missing diagnosis codes from prespecified lists will be performed.

The following covariates will be used for the stratification in patient characterisation.

- Pre-defined indication

The study covariates are described conceptually, and the context or rationale for the choices are provided in this section. The operational definition of the covariates is described in the **Table 5**.

Author(s): [name], [name]

Version: V3.0

Dissemination level: Public

Table 5. Operational definitions of covariates.

Characteristic	Details	Type of variable	Assessment window	Care Settings ¹	Code Type	Diagnosis Position ²	Applied to study populations	Measurement characteristics/validation	Source for algorithm
Age	Age at index date in years	Numeric, continuous	[0,0]	OP	N/A	N/A	individual JAKi ingredient	N/A	N/A
Sex	Biological sex as recorded	Binary, count	[0,0]	OP	N/A	N/A	individual JAKi ingredient	N/A	N/A

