8.7 Study size

No sample size has been calculated for this study. Based on the preliminary feasibility assessment, expected number of subjects to be involved in each data source would be approximately between 600 and 7900.

The feasibility count for each database is as follows: FinOMOP-HILMO (as of 2024-Nov): 2500; IPCI (as of 2024-Nov): 700; IQVIA-DA (as of 2024-Nov): 7900; NLHR (as of 2024-Jul): 2600; VID (as of 2024-Nov): 600

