17. ANNEXES

Appendix I: List of concept definitions

Table s1. Preliminary code list for JAKi

Ingredient concept ID	Drug of interest	ATC code
1758974	Abrocitinib	D11AH08
1510627	Baricitinib	L04AF02
35891916	Filgotinib	L04AF04
1361580	Upadacitinib	L04AF03
42904205	Tofacitinib	L04AF01

Table s2. Preliminary code list for pre-specified indication

Indication	Conc ept ID	Name	Domai n
Inflammatory bowel disease	4626 9838	Abscess of intestine co-occurrent and due to chronic ulcerative pancolitis	Conditi
Inflammatory bowel disease	4626 9848	Abscess of intestine co-occurrent and due to chronic ulcerative rectosigmoiditis	Conditi on
Inflammatory bowel disease	4626 9888	Abscess of intestine co-occurrent and due to Crohn's disease	Conditi on
Inflammatory bowel disease	4627 4073	Abscess of intestine co-occurrent and due to Crohn's disease of large intestine	Conditi on
Inflammatory bowel disease	4626 9878	Abscess of intestine co-occurrent and due to Crohn's disease of small and large intestine	Conditi on
Inflammatory bowel disease	4626 9883	Abscess of intestine co-occurrent and due to Crohn's disease of small intestine	Conditi on
Inflammatory bowel disease	4626 9951	Abscess of intestine co-occurrent and due to ulcerative colitis	Conditi on
Inflammatory bowel disease	6025 94	Acute left-sided ulcerative colitis	Conditi on
Inflammatory bowel disease	4029 372	Acute ulcerative colitis	Conditi on
Inflammatory bowel disease	6025 93	Acute ulcerative pancolitis	Conditi on
Inflammatory bowel disease	6026 07	Acute ulcerative rectosigmoiditis	Conditi on
Inflammatory bowel disease	3671 6986	Arthritis co-occurrent and due to Crohn's disease	Conditi on
Inflammatory bowel disease	4048 1367	Chronic left-sided ulcerative colitis	Conditi on
Inflammatory bowel disease	4047 9837	Chronic ulcerative colitis	Conditi on
Inflammatory bowel disease	1940 77	Chronic ulcerative enterocolitis	Conditi on
Inflammatory bowel disease	7879 9	Chronic ulcerative ileocolitis	Conditi on
Inflammatory bowel disease	4048 2241	Chronic ulcerative pancolitis	Conditi on

Author(s): [name], [name]

Version: V3.0

Inflammatory	7731	Observice of a continuous statistics	Conditi
bowel disease	7	Chronic ulcerative rectosigmoiditis	on
Inflammatory bowel disease	4626 9889	Complication due to Crohn's disease	Conditi on
Inflammatory bowel disease	4626 9874	Complication due to Crohn's disease of large intestine	Conditi on

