Inflammatory bowel disease	4212 992	Exacerbation of Crohn's disease of small intestine	Conditi on
Inflammatory bowel disease	4187 900	Exacerbation of ulcerative colitis	Conditi
Inflammatory bowel disease	1340 490	Exacerbation of ulcerative colitis	Conditi
Inflammatory bowel disease	1340 491	Exacerbation of ulcerative proctocolitis	Conditi
Inflammatory bowel disease	4626 9880	Fistula of intestine due to Crohn's disease of small and large intestine	Conditi
Inflammatory bowel disease	4626 9875	Fistula of large intestine due to Crohn's disease	Conditi
Inflammatory bowel disease	4626 9885	Fistula of small intestine due to Crohn's disease	Conditi
Inflammatory bowel disease	4264 850	Gastrointestinal Crohn's disease	Conditi
Inflammatory bowel disease	4626 9999	History of Crohns disease	Observ ation
Inflammatory bowel disease	4626 9890	Intestinal obstruction due to Crohn's disease	Conditi
Inflammatory bowel disease	4626 9876	Intestinal obstruction due to Crohn's disease of large intestine	Conditi
Inflammatory bowel disease	4626 9881	Intestinal obstruction due to Crohn's disease of small and large intestine	Conditi
Inflammatory bowel disease	4626 9886	Intestinal obstruction due to Crohn's disease of small intestine	Conditi
Inflammatory bowel disease	4259 504	Iritis with ulcerative colitis	Conditi
Inflammatory bowel disease	4048 2865	Left sided ulcerative colitis	Conditi
Inflammatory bowel disease	4301 738	Mild chronic ulcerative colitis	Conditi
Inflammatory bowel disease	4302 002	Moderate chronic ulcerative colitis	Conditi
Inflammatory bowel disease	3184 226	Pancolonic ulcerative colitis	Conditi
Inflammatory bowel disease	4626 9891	Rectal hemorrhage due to Crohn's disease	Conditi
Inflammatory bowel disease	4626 9877	Rectal hemorrhage due to Crohn's disease of large intestine	Conditi
Inflammatory bowel disease	4626 9882	Rectal hemorrhage due to Crohn's disease of small and large intestines	Conditi
Inflammatory bowel disease	4626 9887	Rectal hemorrhage due to Crohn's disease of small intestine	Conditi
Inflammatory bowel disease	4031 048	Severe chronic ulcerative colitis	Conditi
Inflammatory bowel disease	8189 3	Ulcerative colitis	Conditi
Inflammatory bowel disease	4478 3784	Ulcerative colitis in remission	Conditi
Inflammatory bowel disease	4342 656	Ulcerative enterocolitis	Conditi
Inflammatory bowel disease	4025 853	Ulcerative ileocolitis	Conditi
Inflammatory bowel disease	4047 9839	Ulcerative pancolitis	Conditi

Author(s): [name], [name]

Version: V3.0

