Atopic dermatitis	4033 770	Constitutional fingertip eczema	Conditi
Atopic	3711	Exacerbation of constitutional dermatitis due to occupation	Conditi
dermatitis Atopic	0589 4223	'	on Conditi
dermatitis	498	Chronic vesicular eczema of hands and feet	on
Atopic dermatitis	4223 477	Vesicular hand eczema	Conditi
Atopic	4080	Constitutional discoid hand eczema	Conditi
dermatitis Atopic	931 4066		on Conditi
dermatitis	727	Besnier's prurigo	on
Atopic dermatitis	4031 634	Constitutional eczema of foot	Conditi
Atopic dermatitis	4309 200	Allergic inhalant dermatitis	Conditi
Atopic	4031	Chronic podopompholyx	Conditi
dermatitis Atopic	017 3720	Acute vesicular eczema of foot	on Conditi
dermatitis Atopic	3896 4297		on Conditi
dermatitis	495	Chronic constitutional eczema	on
Atopic dermatitis	4031 016	Constitutional eczema of hand	Conditi
Atopic dermatitis	4033 769	Apron pattern of vesicular eczema of hands	Conditi
Atopic dermatitis	4221 832	Acute-on-chronic vesicular eczema of hands	Conditi
Atopic dermatitis	4033 672	Constitutional eczema of hands and feet	Conditi
Atopic	4221	Acute vesicular eczema of hand	on Conditi
dermatitis Atopic	829 4297		on Conditi
dermatitis	494	Acute constitutional eczema	on Conditi
Atopic dermatitis	4290 745	Chronic relapsing vesiculosquamous hand eczema	on
Atopic dermatitis	3654 806	Eczema coxsackium	Conditi on
Atopic dermatitis	4067 178	Podopompholyx	Conditi on
Atopic dermatitis	4223 639	Chronic vesicular eczema of hands	Conditi
Axial spondyloarthriti s	6073 98	Axial spondyloarthritis with peripheral joint involvement	Conditi
Axial spondyloarthriti s	3701 7494	Non-radiographic axial spondyloarthritis	Conditi

Author(s): [name], [name]

Version: V3.0

Axial spondyloarthriti s	3671 6891	Axial spondyloarthritis	Conditi on
Axial spondyloarthriti s	4370 82	Ankylosing spondylitis	Conditi on
Axial spondyloarthriti s	1340 249	Exacerbation of ankylosing spondylitis	Conditi on
Axial spondyloarthriti s	4035 741	Ankylosing spondylitis with multisystem involvement	Conditi
Axial spondyloarthriti s	3720 3959	Ankylosing spondylitis co-occurrent with anterior uveitis	Conditi
Axial spondyloarthriti s	4079 735	Juvenile spondyloarthropathy	Conditi
Axial spondyloarthriti s	4035 614	Ankylosing spondylitis with organ / system involvement	Conditi
Axial spondyloarthriti s	4083 681	Juvenile ankylosing spondylitis	Conditi on
Juvenile idiopathic arthritis	1340 385	Exacerbation of juvenile idiopathic arthritis	Conditi on

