Juvenile idiopathic arthritis	4132 810	Juvenile seronegative polyarthritis	Conditi on
Juvenile idiopathic arthritis	4132 809	Juvenile seropositive polyarthritis	Conditi
Juvenile idiopathic arthritis	4079 734	Juvenile psoriatic arthritis with psoriasis	Conditi on
Juvenile idiopathic arthritis	6080 43	Rheumatoid factor negative and anti-citrullinated protein antibody negative juvenile polyarthritis	Conditi
Juvenile idiopathic arthritis	4079 733	Juvenile psoriatic arthritis	Conditi on
Juvenile idiopathic arthritis	6080 42	Rheumatoid factor positive and anti-citrullinated protein antibody negative juvenile polyarthritis	Conditi on
Juvenile idiopathic arthritis	6080 44	Rheumatoid factor negative and anti-citrullinated protein antibody positive juvenile polyarthritis	Conditi on
Juvenile idiopathic arthritis	4035 612	Early onset polyarticular juvenile chronic arthritis	Conditi on
Juvenile idiopathic arthritis	6080 41	Rheumatoid factor positive and anti-citrullinated protein antibody positive juvenile polyarthritis	Conditi
Juvenile idiopathic arthritis	4083 680	Juvenile psoriatic arthritis without psoriasis	Conditi

P3-0	C1-(001	Study	Prof	tocol

Version: V3.0

Dissemination level: Public

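### The inflammatory bowel disease code list shows only Crohn's disease and ulcerative colitis terms, so users with only a generic or indeterminate record become unknown indication

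*Protocol*

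**What the plan says.** Section 8.6.3 names inflammatory bowel disease as one of seven pre-specified indications. An indication is assigned from any matching record before the first exposure to the ingredient, and one user may have several. The eighth category is a residual: "Unknown indication (defined as none of the predefined indications were found". Time from first diagnosis to initiation is estimated separately for each indication.

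The codes are in Appendix I, Table s2, titled "Preliminary code list for pre-specified indication". Under inflammatory bowel disease the rows run alphabetically from intestinal abscess terms to "Ulcerative pancolitis", after which the row names are broken in the available text. Within the legible rows, "History of Crohns disease" is followed immediately by "Intestinal obstruction due to Crohn's disease".

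Two checks bear on omitted codes. Section 8.6.3 plans a large-scale characterisation to look for diagnosis codes missing from the lists. Section 10 plans review of candidate codes by two clinical epidemiologists, and CohortDiagnostics or a similar tool. Section 14 says that the large-scale characterisation will be shown only in the interactive dashboard.

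**The concern.** The stratum carries the name of the whole disease group, but its list appears to cover only the two named diseases within it. A record of inflammatory bowel disease without further specification, or of indeterminate colitis, matches nothing in the list.

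Indication is the stratifier of Objective 2, and section 6 says that the study is meant to inform the feasibility of future safety studies. Counts by indication are therefore a main product. They will be thin in places: section 8.7 expects about 700 exposed users in IPCI and 600 in VID, to be spread over 5 ingredients × 8 indication categories = 40 cells. Section 8.8 masks counts below 5, and section 8.9 rules out pooling across databases. Users moved from a named stratum to the residual reduce the apparent feasibility for that stratum and make the unknown category harder to interpret.

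**Working it through.** The protocol states no figure to reproduce. The check is a reading of Table s2 and of the rules that use it.

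**1. Content of the legible list.** Each inflammatory bowel disease row, up to and including "Ulcerative pancolitis", was sorted by whether its name contains Crohn or ulcerative.

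| Rows | Count |
|---|---|
| Contain Crohn | 49 |
| Contain ulcerative | 28 |
| Contain neither | 0 |
| Total | 49 + 28 = 77 |

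**2. Is the gap only an effect of unreadable rows?** The 77 names are in strict alphabetical order. Indeterminate colitis and inflammatory bowel disease would both sort between "History of Crohns disease" and "Intestinal obstruction due to Crohn's disease". Those two rows are adjacent and legible. The broken block starts only after "Ulcerative pancolitis", so a generic term could sit there only if it had been added out of order.

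**3. Comparison with the other lists.** The lists for rheumatoid arthritis, alopecia areata, atopic dermatitis, axial spondyloarthritis and juvenile idiopathic arthritis each include the concept that names the stratum. The psoriatic arthritis rows fall in the broken block and cannot be checked. Of the six lists that can be read, inflammatory bowel disease is the only one without its own name.

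**4. Effect on classification.** In one database and for one ingredient, let n be the users with any recorded form of inflammatory bowel disease before the index date. Let g be the share of them with only generic or indeterminate records, and o the share of those who also have another listed indication.

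- Stratum count as written: n(1 − g), which is short by n·g.
- Added to unknown indication: n·g·(1 − o).

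A specific code recorded on or after the index date does not help, because the assessment window in Table 5 ends on the day before.

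**5. Effect on time to initiation.** Take a user with a generic record at t1, a specific record at t2 > t1, and initiation at t3 > t2. The list yields t3 − t2 where t3 − t1 is wanted, so the interval is too short by t2 − t1.

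The protocol gives no value for g, o or t2 − t1. The direction is therefore fixed, but the size cannot be computed.

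**The case against.** The strongest reply is that the list is labelled preliminary and the protocol already plans to look for omitted codes in two ways. That is right, and it softens the point. It does not remove it, because no section says that codes found by these checks will be added, or by when. The timing is also tight: version 3.0 is dated 29/01/2025 and section 5 puts execution in January to February 2025. A gap that is visible on the page need not wait for a diagnostic run.

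A second reply is that absence is inferred from alphabetical order while part of the table is unreadable. This stands as a caveat. The rheumatoid arthritis list ends with condition rows placed after its measurement rows, so late additions do occur in this table. A generic term in the broken rows is unlikely but cannot be excluded.

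A third is that the restriction to ulcerative colitis and Crohn's disease may be deliberate. The protocol never says so, and the drafting is otherwise broad: the same list includes Crohn's disease of the gums and a history-of-disease observation.

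It is also fair that one earlier specific code is enough to place a user in the stratum, so the misclassification affects only those who never had one before the index date.

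A reader might go further and infer that the juvenile idiopathic arthritis list has the same defect, since it holds "Juvenile psoriatic arthritis with psoriasis" but not "Juvenile ankylosing spondylitis" or juvenile spondyloarthropathy. The documents do not support that. Both codes are in Table s2 under axial spondyloarthritis, so users who carry them have a named indication and cannot become unknown. Those who also have a juvenile idiopathic arthritis code are counted in both strata. Which named stratum should hold these codes is a classification preference.

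**Conclusion.** The point holds for inflammatory bowel disease. If the legible list is what will be run, users with only a generic or indeterminate record and no other listed indication are classed as unknown. Users whose generic record came first have their time from diagnosis understated. The conclusion rests on the broken rows containing no late generic entry, and on the list being executed without these additions.

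The size is unknown. A reader might be tempted to attach a percentage, or to assume that the effect differs between databases because their care settings differ. The protocol reports no coding frequencies and no counts by indication, so neither can be claimed. It is a specific, correctable gap in a preliminary list, and it does not touch Objective 1, which does not use indication.

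**What to change.** Before execution, add the generic inflammatory bowel disease concept and the indeterminate colitis concept to the inflammatory bowel disease list in Table s2. Report users who enter only through them as an unspecified subgroup. If the stratum is meant to cover ulcerative colitis and Crohn's disease only, say so in section 8.6.3 and rename it.

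One sentence in section 10 should state how codes found by the planned checks are accepted into the lists, and that the lists are frozen before the final package is released.

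The cost is two concepts and a few lines of text, with no new data. Unspecified codes are slightly less specific, which is the reason for showing them separately. Listing the two juvenile spondyloarthritis codes under juvenile idiopathic arthritis as well is optional, since section 8.6.3 allows multiple indications.

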Appendix II: ENCePP checklist for study protocols

Study title:

Characterising the use of JAK inhibitors in Europe: a Drug Utilisation Study

EU PAS Register® number: N/A

Study reference number (if applicable): P3-C1-001

Section 1: Milestones	Yes	No	•	Section Number
1.1 Does the protocol specify timelines for				
1.1.1 Start of data collection ²	x			8.5
1.1.2 End of data collection ³	х			8.5
1.1.3 Progress report(s)			X	
1.1.4 Interim report(s)			X	
1.1.5 Registration in the EU PAS Register®			х	
1.1.6 Final report of study results.	х			5

Section 2: Research question	Yes	No	N/A	Section Number
2.1 Does the formulation of the research question and objectives clearly explain:				
2.1.1 Why the study is conducted? (e.g. to address an important public health concern, a risk identified in the risk management plan, an emerging safety issue)	x			6, 7
2.1.2 The objective(s) of the study?	х			7
2.1.3 The target population? (i.e. population or subgroup to whom the study results are intended to be generalised)	х			7
2.1.4 Which hypothesis(-es) is (are) to be tested?			x	

DARWIN M	P3-C1-001 Study Protocol	
©EU/V	Author(s): [name], [name]	Version: V3.0
20 1		Dissemination level: Public
2.1.5 If applicable, that	there is no a priori hypothesis?	x

Comments:

Section 3: Study design	Yes	No	N/A	Section Number
3.1 Is the study design described? (e.g. cohort, case-control, cross-sectional, other design)	х			8.1
3.2 Does the protocol specify whether the study is based on primary, secondary or combined data collection?	х			8.2
3.3 Does the protocol specify measures of occurrence? (e.g., rate, risk, prevalence)	х			8.8
3.4 Does the protocol specify measure(s) of association? (e.g. risk, odds ratio, excess risk, rate ratio, hazard ratio, risk/rate difference, number needed to harm (NNH))			х	
3.5 Does the protocol describe the approach for the collection and reporting of adverse events/adverse reactions? (e.g. adverse events that will not be collected in case of primary data collection)			х	

Section	n 4: Source and study populations	Yes	No	N/A	Section Number
4.1	Is the source population described?	х			8.2, 8.5
4.2	Is the planned study population defined in terms of:				
4.2.1 S	itudy time period	х			8.5
4.2.2 A	Age and sex	х			8.6.3
4.2.3 C	Country of origin	х			8.2
4.2.4 C	Disease/indication	x			8.6.3

D2 C1	001	Chinds	Duct	
P3-C1	-OOT	Stuav	/ Proi	.OCOI

Version: V3.0

Dissemination level: Public

4.2.5 Duration of follow-up	x		8.8.2	
4.3 Does the protocol define how the study population will be sampled from the source population? (e.g. event or inclusion/exclusion criteria)	x		8.5	

Comments:

Section 5: Exposure definition and measurement	Yes	No	N/A	Section Number
5.1 Does the protocol describe how the study exposure is defined and measured? (e.g. operational details for defining and categorising exposure, measurement of dose and duration of drug exposure)	x			8.6.1
5.2 Does the protocol address the validity of the exposure measurement? (e.g. precision, accuracy, use of validation substudy)			х	
5.3 Is exposure categorised according to time windows?			х	
5.4 Is intensity of exposure addressed? (e.g. dose, duration)	x			8.8.2
5.5 Is exposure categorised based on biological mechanism of action and taking into account the pharmacokinetics and pharmacodynamics of the drug?			х	
5.6 Is (are) (an) appropriate comparator(s) identified?			х	

Section 6: Outcome definition and measurement	Yes	No		Section Number
6.1 Does the protocol specify the primary and secondary (if applicable) outcome(s) to be investigated?	x			8.6.2
6.2 Does the protocol describe how the outcomes are defined and measured?			х	

6.3 Does the protocol address the validity of outcome measurement? (e.g. precision, accuracy, sensitivity, specificity, positive predictive value, use of validation sub-study)	,	Х	
6.4 Does the protocol describe specific outcomes relevant for Health Technology Assessment? (e.g. HRQoL, QALYs, DALYS, health care services utilisation, burden of disease or treatment, compliance, disease management)		х	

Comments:

Section 7: Bias	Yes	No	N/A	Section Number
7.1 Does the protocol address ways to measure confounding? (e.g. confounding by indication)			х	
7.2 Does the protocol address selection bias? (e.g. healthy user/adherer bias)			х	
7.3 Does the protocol address information bias? (e.g. misclassification of exposure and outcomes, time-related bias)			х	

Comments:

Section 8: Effect measure modification	Yes	No	-	Section Number
8.1 Does the protocol address effect modifiers? (e.g. collection of data on known effect modifiers, sub-group analyses, anticipated direction of effect)	х			8.6.3

Section 9: Data sources	Yes	No	-	Section Number	
-------------------------	-----	----	---	-------------------	--

P3-C1-001	Study	Protocol
-----------	-------	----------

Version: V3.0

Dissemination level: Public

9.1 Does the protocol describe the data source(s) used in the study for the ascertainment of:			
9.1.1 Exposure? (e.g. pharmacy dispensing, general practice prescribing, claims data, self-report, face-to-face interview)	х		8.2
9.1.2 Outcomes? (e.g. clinical records, laboratory markers or values, claims data, self-report, patient interview including scales and questionnaires, vital statistics)		x	
9.1.3 Covariates and other characteristics?	Х		8.6.3
9.2 Does the protocol describe the information available from the data source(s) on:			
9.2.1 Exposure? (e.g. date of dispensing, drug quantity, dose, number of days of supply prescription, daily dosage, prescriber)	х		8.2
9.2.2 Outcomes? (e.g. date of occurrence, multiple event, severity measures related to event)		х	
9.2.3 Covariates and other characteristics? (e.g. age, sex, clinical and drug use history, co-morbidity, co-medications, lifestyle)	х		8.2
9.3 Is a coding system described for:			
9.3.1 Exposure? (e.g. WHO Drug Dictionary, Anatomical Therapeutic Chemical (ATC) Classification System)	х		8.6.1
9.3.2 Outcomes? (e.g. International Classification of Diseases (ICD), Medical Dictionary for Regulatory Activities (MedDRA))		х	
9.3.3 Covariates and other characteristics?	Х		8.8.2
9.4 Is a linkage method between data sources described? (e.g. based on a unique identifier or other)		x	

Section 10: Analysis plan	Yes	No	N/A	Section
				Number

[figure not shown]

10.1 choice	Are the statistical methods and the reason for their described?	x		8.8
10.2	Is study size and/or statistical precision estimated?		х	
10.3	Are descriptive analyses included?	Х		8.8
10.4	Are stratified analyses included?	Х		8.8
10.5 confou	Does the plan describe methods for analytic control of inding?		х	
10.6 outcon	Does the plan describe methods for analytic control of ne misclassification?		х	
10.7 data?	Does the plan describe methods for handling missing		х	
10.8	Are relevant sensitivity analyses described?		Х	

Comments:

Section 11: Data management and quality control	Yes	No	,	Section Number
11.1 Does the protocol provide information on data storage? (e.g. software and IT environment, database maintenance and anti-fraud protection, archiving)	x			9
11.2 Are methods of quality assurance described?	х			10
11.3 Is there a system in place for independent review of study results?			x	

Section 12: Limitations	Yes	No	-	Section Number
12.1 Does the protocol discuss the impact on the study results of:				

12.1.1 Selection bias?		X	
12.1.2 Information bias?	Х		11
12.1.3 Residual/unmeasured confounding?		X	
(e.g. anticipated direction and magnitude of such biases, validation sub-study, use of validation and external data, analytical methods).			
